HPV	Human papillomavirus
hr-HPV	High risk HPV
ICC	Invasive cancer of the cervix
ICF	Informed consent form
IM	Intramuscular
PID	Participant identification number
Q-HPV	Quadrivalent human papillomavirus – Gardasil®
REB	Research ethics board
SAE	Serious Adverse Event
SID	Secondary identifier
SOP	Standard of practice

PROTOCOL

Long Term Immune Memory Responses to Human Papillomavirus (HPV) Vaccination Following 2 Versus 3 Doses of Quadrivalent HPV Vaccine

1.0 INTRODUCTION/BACKGROUND

Cervical cancer is the second most commonly diagnosed cancer among females worldwide and affects over half a million women globally each year. (1) In Canada, cervical cancer is the second most common cancer in women aged 20-49 (2). Human papillomavirus (HPV) is known to be the etiological agent of cervical cancer and causes cancer by targeting the basal cell of squamous epithelium located in the transformation zone of the cervix (3). HPV types 16, 18, 31, 33, 35, 45, 51, 52, and 56 have been consistently associated with severe grades of cervical intraepithelial neoplasia (CIN) and invasive carcinoma and are thus classified as high risk HPV (hr-HPV) (4). Sexual activity and age of first sexual intercourse are among the primary determinants of HPV infection and therefore interventions aimed at preventing acquisition of oncogenic HPV infection and cervical cancer should begin before the onset of first sexual activity (5-7).

Persistent HPV Infection: HPV is a highly prevalent infection, and it is estimated that over 75% of women have a cervical HPV infection at some time in their life. (8). Natural history studies show that most cervical infections with hr-HPV clear spontaneously (9), but in 10-20% of women, these infections persist and it is these persistent infections that can lead to grade 2/3 cervical intraepithelial neoplasm (CIN) (10) and eventually invasive cancer of the cervix (ICC) (11). Cross sectional prevalence studies show that the burden of HPV infection is concentrated in younger women (<30), but these infections in younger women are often transient and most will clear spontaneously (12). Meta-analyses indicate that women who have hr-HPV types 16 and 18 persisting for 6-12 months or more have significantly increased risk of developing incident high grade CIN (13).

HPV vaccine and cervical cancer prevention: Until recently, screening and treatment of cervical abnormalities, through public health programs, were the primary methods of controlling cervical cancer. However, the availability of the HPV vaccine has changed the focus of cervical cancer prevention, and primary prevention of cervical cancer is now a critical opportunity (14-15). Gardasil® (Q-HPV) is approved for a 3 dose schedule at 0, 2 and 6 months or a 2 dose schedule at 0 and 6 months, and is highly efficacious and immunogenic (16-17). Phase III trials have shown that a three-dose regimen of Q-HPV is 98 - 100% effective in preventing HPV 16, and 18 related CIN2/3 out to 5 years (16-18). Cervarix® (GlaxoSmithKline), a bivalent HPV vaccine approved in Canada (19), is also highly immunogenic and studies have shown 100% effective out to 60 months in preventing HPV 16 and 18 related CIN2/3 with geometric mean titers (GMTs) substantially higher than natural infection titers.

Current HPV Vaccination Programs in Canada: All Canadian provinces have school based HPV vaccine program for girls. Although all programs aim to provide HPV vaccine prior to girls' sexual debut, each jurisdiction incorporated the HPV vaccine into existing school based programs and thus, nationally, girls are given HPV vaccine during different grades. In addition, some provinces have catch up programs. In 2008, Quebec launched its program using a 2 dose program (0 and 6 months; plus 1 booster at 60 months) for girls in Grade 4 (20). In 2010, based on findings from the clinical trial BCGOV01(21-23), British Columbia

started using 2 doses in its Grade 6 program with a booster possible at Grade 9 or 11. Most other jurisdictions now use 2 dose programs following the approved HPV vaccine schedule.

Immunogenicity: HPV vaccine is highly immunogenic (1). Peak antibody concentrations at Month 7 range from 1 to 4 times greater than those found with natural HPV infections. The antibodies to HPV 6, 11, 16 & 18 (the four types contained in the vaccine) typically increase after each vaccine dose, and a peak response is achieved after the final dose. Concentrations wane in the following 12-18 months and then stabilize. Challenges with HPV type specific antigens at 60 months after dose 1 show an anamnestic response for all four subtypes, with antibody levels rising within 3-5 days to levels greater than those achieved at the peak in the initial immunization schedule (24-265).

The long-term goal is to understand the memory response to HPV vaccination. Although memory responses can be detected shortly after immunization, the best approach to measure the long-lasting anamnestic response is to challenge with a booster dose years (> 5) after the original exposure.

2.0 OBJECTIVES

Primary objective:

- To compare the B memory and plasmablast populations between girls and young women that received either a primary 2 or 3 dose series, who are then challenged with a subsequent dose after 120 months.

Secondary objectives:

- To compare the extent of somatic hypermutation and the variable gene usage between girls that received either a primary 2 or 3 dose series.
- To compare the serum antibody responses to HPV 6, 11, 16 & 18 at month 120 in females that received either a primary 2 or 3 dose series, who are then challenged with a subsequent dose.

3.0 STUDY DESIGN AND PARTICIPANT OVERVIEW

This is a single center, interventional study to evaluate long term memory response to HPV 6, 11, 16 & 18. Memory response will be assessed by measuring seroprotection 8-10 years post Q-HPV vaccination and to challenge with a booster dose of HPV9 vaccine (Gardasil® 9, Merck Canada, Inc.) years after the original exposure to measure the long-lasting anamnestic response. This is a 3 arm study with 6 girls per group:

Group 1: girls who received 2 doses of Q-HPV vaccine at 0, 6 month schedule 8-10 years ago when they were between 9-13 years of age at the time of the first dose.

Group 2: girls who received 3 doses of Q-HPV vaccine at 0, 2, 6 month schedule 8-10 years ago when they were between 9-13 years of age at the time of the first dose.

Group 3: young women who received 3 doses of Q-HPV vaccine at 0, 2, 6 month schedule 8-10 years ago when they were between 16-26 years of age at the time of the first dose.

3.1 Study plan

At the first visit, enrolled participants will have a health assessment, provide a blood sample (45ml), and a booster dose of licensed HPV9 vaccine will be given.

At the second visit, 7 days later, and again at the third visit at 30 days, a 45ml blood test to assess the response to the booster vaccine will be drawn.

Participants will be offered two additional doses of HVP9 vaccine at 2 and 6 months as a courtesy to complete the vaccine series (27, 28). The visits are optional and no additional serologic testing will be done.

Duration of study for each participant

The study will include three regular visits and two optional visits. At the first visit, about 60 minutes will be required to complete informed consent, record demographic and health information, draw a blood sample, vaccinate, and to observe vaccinees for 15 minutes afterward to detect and treat any rare allergic reaction. The subsequent visits for a follow-up blood test will require only about 30 minutes, to confirm ongoing consent and eligibility, and to draw a post vaccination blood sample. The two optional vaccination visits to complete will require 20 minutes including a 15 minute post vaccination observation period.

The time commitment to complete the study will be 2 hours. Study duration for each participant will be 1 month.

For participants who choose to return for additional HPV9 vaccination at 2 and 6 months to complete the vaccine series, the time to complete will be 2.6 hours over 6 months.

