3.3 Schedule of Events

Visit Activities Visit Window	Telephone	Visit 1 Day 0	Visit 2 Day 7 +/- 1d	Visit 3 Day 30 +/- 3d	Optional visit 4 2 months	Optional visit 5 6 months
Recruitment/Screening	X					
Eligibility Inclusion/Exclusion		X	ongoing	ongoing		
Informed Consent		X	ongoing	ongoing		
Blood Sample		X	X	X		
Pregnancy Test		X		X		
HPV9 Vaccine		X			X	X
Adverse Events			X	X		

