4.4 Health assessments

A health history will be reviewed at Visit 1 to identify any current health conditions. The health assessment will be sufficiently detailed to confirm eligibility to participate. Height, weight and oral temperature will be obtained. If oral temperature is greater than or equal to 38.0 C then immunization will be delayed until the participant has been afebrile for at least 24 hours. A urine sample for pregnancy testing will be performed at Visit 1 and Visit 3, and concomitant medications and contraindications to immunization will also be sought prior to immunization.

At visit 2 and 3, an interval health history will be obtained to confirm ongoing eligibility.

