4.7.2 Reporting of adverse events following immunization

Surveillance for provincially reportable adverse events following immunization (AEFI) will conform to recommended practices in British Columbia. At Visits 2 and 3 participants will be asked about any AEFI of concern to them, especially if medical consultation was required. Adverse events that qualify for reporting will be reported to British Columbia Centre for Disease Control using the provincial AEFI reporting form. Participants will be advised when reporting is done on their behalf by study staff.

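### No adverse-event enquiry is scheduled at or after the optional 2- and 6-month HPV9 doses, and the end of SAE reporting is undefined for participants who take them

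*Protocol*

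**What the plan says.** All references are to the Protocol.

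- **Doses.** At Visit 1 "a booster dose of licensed HPV9 vaccine will be given". Section 3.1 continues: "Participants will be offered two additional doses of HVP9 vaccine at 2 and 6 months as a courtesy to complete the vaccine series". Of these later attendances it says: "The visits are optional and no additional serologic testing will be done". The Schedule of Events (3.3) marks the HPV9 vaccine row at Visits 1, 4 and 5.
- **Adverse-event enquiry.** The "Adverse Events" row in 3.3 is marked at Visits 2 and 3 only. Section 4.7.2 agrees: "At Visits 2 and 3 participants will be asked about any AEFI of concern to them".
- **Other safety provisions.** Section 4.7.1 requires at least 15 minutes of observation after vaccination, and 3.1 builds the same period into each optional visit. Section 4.7.2 also commits to provincial surveillance of reportable events, and 5.3 describes reporting them as a legal obligation. None of these is limited to particular visits.
- **SAEs.** Section 4.7.3 asks participants to notify the investigator of SAEs that occur during their enrolment. It does not say when enrolment ends.
- **Duration.** Section 3.1 states: "Study duration for each participant will be 1 month". It also counts the two optional visits as part of the study and gives 6 months for participants who take the extra doses.
- **Pregnancy testing.** Section 4.4: "A urine sample for pregnancy testing will be performed at Visit 1 and Visit 3". The schedule in 3.3 shows the same two visits.

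**The concern.** Vaccine is given under the protocol at three visits, but the scheduled safety questions follow only the first dose. The last enquiry comes at Visit 3, before either optional dose. Participants who accept the offer come back in person at Visits 4 and 5, yet the plan does not have staff ask what has happened since the previous visit or dose.

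The SAE provision might be expected to fill this gap, but it depends on the participant coming forward and on a period whose end is not stated. If participation ends at 1 month, SAE reporting stops before both optional doses. If it ends at 6 months, it stops at about the time of the last one. Neither reading gives a stated reporting period after the final dose.

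What is at stake is participant safety and the completeness of the safety record for the optional doses. A non-serious event, or a serious one that the participant does not think to report, could go unrecorded although the site has the participant in front of it.

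**Working it through.** **Inputs**

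- Participants: "This is a 3 arm study with 6 girls per group" (section 3.0), so 3 × 6 = 18.
- Doses per participant: 1 at Visit 1, plus 0 to 2 optional (3.1, 3.3).
- Last scheduled adverse-event enquiry: Visit 3, day 30 ± 3 (3.3, 4.7.2).
- Uptake of the optional doses: not stated, so a range is shown.

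**The plan's own figures.** The documents give no dose total or dose share. The related figures they do give are visit times in 3.1, and these reproduce:

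- Regular visits: (60 + 30 + 30) / 60 = 2.0 hours; the plan states 2 hours.
- With both optional visits: (60 + 30 + 30 + 2 × 20) / 60 = 2.67 hours; the plan states 2.6 hours, which is the same figure truncated.

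The second figure shows that the plan costs the optional visits as part of a participant's time commitment.

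**Timing.** Counting 30.44 days to a month from Visit 1, the optional doses fall at 2 × 30.44 = 60.9 days and 6 × 30.44 = 182.6 days. Both come after the last enquiry, which is at day 33 at the latest within its window. The 6-month dose comes about 5 months after it (6 − 1).

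**Share of doses with no later scheduled enquiry.** Let u4 and u5 be the numbers taking the dose at Visits 4 and 5, with all 18 vaccinated at Visit 1:

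share = (u4 + u5) / (18 + u4 + u5)

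| Assumed uptake | u4, u5 | Share |
|---|---|---|
| None | 0, 0 | 0/18 = 0% |
| Half take both | 9, 9 | 18/36 = 50% |
| All take the first only | 18, 0 | 18/36 = 50% |
| Two thirds take both | 12, 12 | 24/42 = 57.1% |
| All take both | 18, 18 | 36/54 = 66.7% |

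**Visit by visit, from 3.3**

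| | V1 | V2 | V3 | V4 (optional) | V5 (optional) |
|---|---|---|---|---|---|
| Vaccine | yes | | | yes | yes |
| Adverse-event enquiry | | yes | yes | | |

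The text of 4.7.2 gives the same two enquiry visits, so the blank cells at Visits 4 and 5 are not an artefact of how the table was read.

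**The case against.** The strongest reply has four parts.

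1. **Safety coverage does not stop at Visit 3.** This stands. Observation after vaccination applies to every dose and is repeated for the optional visits, and the commitment to provincial surveillance carries no visit limit. A reader might infer that adverse events are not collected at all for the optional doses; the documents do not support that. What is missing is a scheduled enquiry. Fifteen minutes of observation catches only immediate reactions, and the only enquiry that 4.7.2 describes is at Visits 2 and 3.

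2. **The optional doses are not plainly outside the study.** This also stands. Section 3.1 states 1 month, but it also includes the optional visits in the study and gives 6 months for those who take them. The 1-month figure is a study duration; no section equates it with enrolment. A reader might infer that SAEs after the later doses are excluded, but the documents leave the matter undefined.

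3. **The pregnancy and eligibility provisions do not contradict each other.** Sections 3.3 and 4.4 agree on testing at Visits 1 and 3, and 4.4 says contraindications are sought before immunization without expressly confining that to Visit 1. The absence of a test at Visits 4 and 5 is therefore not shown to be an error. What remains open is narrower: the contraception requirement (4.3.1) and the pregnancy exclusion (4.3.2) run for the length of the study or trial, and that length is the undefined quantity.

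4. **The consequence for the trial's results is nil.** This stands. The vaccine is licensed, the extra doses are a courtesy, section 2.0 has no safety objective, and neither section 6.0 nor the SAP plans a safety analysis. All blood is drawn by Visit 3. It limits the weight of the point but does not remove it, because the protocol undertakes to ask about events after the first dose and gives no reason for not asking after the others.

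**Conclusion.** The point holds as a gap in scheduled enquiry together with an undefined reporting period. Under the plan as written, no adverse-event question is scheduled at or after the 2- and 6-month doses, and the end of SAE reporting cannot be determined for participants who take them.

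The share of protocol doses affected lies between 0% and 67%. The upper figure is a ceiling that requires all 18 participants to take both optional doses, and it should not be read as an expected value. The range assumes that 18 are enrolled and that all receive the Visit 1 dose.

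No immune endpoint, estimate or planned analysis changes. The case for acting is that the change is nearly free and improves participant safety and the safety record.

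**What to change.** For data collection:

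- In 3.3, mark the adverse-event row at Visits 4 and 5, and amend 4.7.2 to match, so that events since the previous visit or dose are asked about while the participant is present.
- In 3.1 and 4.7.3, state that for participants taking optional doses SAE reporting runs to a defined point after their last study-supplied dose.

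The second change is needed because an enquiry at Visit 5 cannot cover what follows the Visit 5 dose. At full uptake the first change alone reduces the doses with no later scheduled enquiry from 36 to 18 of 54 (33%); the remaining 18 would rely on the defined SAE reporting period. If the sponsor wants an active question after the final dose as well, one contact at that point would provide it.

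The cost is a protocol edit with ethics board approval (7.1), a few extra minutes at two visits that already take place, and a longer reporting period for those who take the optional doses.

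Separately, the investigator should reconcile 3.1, 3.3, 4.3.1, 4.3.2 and 4.4 on which eligibility, contraception and pregnancy provisions apply at the optional doses. No clinical rule is proposed here.

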3.2 Study population

Participants will be females who were immunized with 2 or 3 doses of Q-HPV vaccine at ages 9-13 and 16-26 years.

3.3 Schedule of Events

Visit Activities Visit Window	Telephone	Visit 1 Day 0	Visit 2 Day 7 +/- 1d	Visit 3 Day 30 +/- 3d	Optional visit 4 2 months	Optional visit 5 6 months
Recruitment/Screening	X					
Eligibility Inclusion/Exclusion		X	ongoing	ongoing		
Informed Consent		X	ongoing	ongoing		
Blood Sample		X	X	X		
Pregnancy Test		X		X		
HPV9 Vaccine		X			X	X
Adverse Events			X	X		

4.0 CONDUCT OF STUDY

4.1 Good Clinical Practice

4.1.1 Institutional Review Board

This study is being conducted according to the Good Clinical Practice Guidelines of the International Committee on Harmonization (ICH Guidance Document *E6: Good Clinical Practice (GCP): Consolidated Guideline*). The investigators will utilize the Research Ethics Board at BC Children's and Women's Hospitals, which conforms to section 3 regarding Responsibilities; Composition, Functions and Operations; Procedures; and Records.

4.1.2 Enrollment

Volunteers will be screened for eligibility before the first visit is scheduled. Participants will provide written informed consent for themselves. The informed consent process must be completed, with the informed consent form (ICF) signed and dated before any procedures specified in this protocol are performed.

Prior to beginning the study, the investigator will have REB written approval of the ICF and any other written information to be provided to participants. Both the informed consent discussion and the ICF will include the necessary content to meet the Good Clinical Practice Guidelines.

4.1.3 Regulatory considerations

Only vaccine supplied for use in this trial will be administered.

4.1.4 Monitoring

To ensure that the trial is conducted and documented appropriately, the following activities will be carried out:

- The site will have up to date **standards of practice** regarding REB approval processes; essential document storage; vaccine handling and storage; determination of eligibility; study staff delegation, qualification, training processes; and the process for Informed Consent.
- **Refrigerator temperature stability** will be demonstrated prior to receiving study vaccine and documented daily thereafter to ensure that the study refrigerator maintains a temperature within 2-8 °C.
- The site will have an **Essential Documents** box specific to this study, to contain copies of the REB approvals and amendments, refrigerator assessments, source documents, AEFI reports, waivers, and vaccine supply inventory.
- The site will devise **source documents** appropriate to this study.
- **Protocol compliance checks** will be made, including: consent date and time, visit dates; immunization details (product, date, time, administration method, cold chain compliance); blood sample details (sample volume, date and time, storage temperature); completion of data.

- **Training** of participating staff and investigators will be conducted prior to study start.

4.2 Recruitment and volunteer identification

4.2.1 Recruitment

This is a closed recruitment cohort from the BCGov01 study and, if needed, girls and young women who were immunized in the BC provincial program who have given permission to be contacted about future studies with the VEC.

4.3 Eligibility criteria

4.3.1 Inclusion criteria

The participant must meet all of the following inclusion criteria to participate in this study. Inclusion criteria include:

- Written informed consent provided by the participant.
- Participant whom the investigator believes can and will comply with the requirements of the protocol.
- General good health.
- Immunized with Q-HPV vaccine between the ages of 9-13 or 16 to 26 years on the BCGov01 study or the BC provincial program.
- Participant who is of child bearing potential must be willing to ensure that they or their partner use effective contraception during the study. Examples of effective methods of birth control include:

- * Abstinence (no sexual activity)
- * Hormonal contraceptives including oral, injectable, implants & skin patches
- * Intrauterine device (IUD)
- * Male partner sterilization
- * Male condom combined with a vaginal spermicide (foam, gel, film, cream or suppository)
- * Male condom combined with a female diaphragm, whether with or without a vaginal spermicide (foam, gel, cream, or suppository)
- * Adequate contraception does not apply to participants with same sex partners, when this is their preferred and usual lifestyle

4.3.2 Exclusion criteria

The participant may not enter the study if any of the following exclusion criteria apply:

- Received more than 3 doses of Q-HPV vaccine
- Received any doses of HPV9 vaccine

- Systemic hypersensitivity to Q-HPV or HPV9 vaccines or severe reaction to any previous dose of Q-HPV vaccine
- Receipt of blood or blood product within 3 months prior to Visit 1
- Receipt of a live vaccine within 28 days or an inactive vaccine within 14 days of Visit 1
- Immune compromise resulting from disease or immunosuppressive systemic medication use within 3 months prior to Visit 1
- Inadequate participant fluency in English to provide fully informed consent
- Participant who is currently pregnant or planning a pregnancy during the course of the trial

4.4 Health assessments

A health history will be reviewed at Visit 1 to identify any current health conditions. The health assessment will be sufficiently detailed to confirm eligibility to participate. Height, weight and oral temperature will be obtained. If oral temperature is greater than or equal to 38.0 C then immunization will be delayed until the participant has been afebrile for at least 24 hours. A urine sample for pregnancy testing will be performed at Visit 1 and Visit 3, and concomitant medications and contraindications to immunization will also be sought prior to immunization.

At visit 2 and 3, an interval health history will be obtained to confirm ongoing eligibility.

